2. To compare type 1 and 3 immunogenicity of one or three doses of bOPV with the same number of doses of bOPV co-administered with nOPV2.
3. To assess the presence of fecal viral shedding (as determined by real-time RT-PCR) over time following one dose of nOPV2, bOPV, or co-administered nOPV2 and bOPV.
4. To estimate household transmission of nOPV2 by assessing the presence of fecal viral shedding (as determined by real-time RT-PCR) among siblings of vaccine recipients.
5. To assess the occurrence and genomic characteristics of intertypic recombinants in stool specimens of vaccine recipients and siblings after one dose of nOPV2 given with or without bOPV.

Methods:

This is an open-label randomized clinical trial. Vaccine recipient participants will be enrolled and randomized at 6 weeks to one of three arms:

- A: nOPV2 @ 6, 10, and 14 weeks
- B: nOPV2 + bOPV @ 6, 10, and 14 weeks
- C: bOPV @ 6, 10, and 14 weeks

For each vaccine recipient, a sibling below 10 years of age will be selected for participation as a sibling.

Outcome measures/variables:

Poliovirus antibody titers to types 1, 2 and 3 will be measured in sera extracted from vaccine recipient blood collected at 6, 10, 14, and 18 weeks. Antibody titers at 6 weeks of age will be the assumed starting point for the expected decline in maternal antibody assuming a half-life of 28 days. Shedding of poliovirus will be measured from stool specimens collected from vaccine recipients and one sibling each at 1, 2, and 4 weeks post-vaccination in Arm A and at 2 and 4 weeks post-vaccination in Arms B and C. Intertypic recombinants will be characterized in a subset of stool specimens collected from vaccine recipients and siblings.

Description of the Research Project

Hypothesis to be tested:

Does this research proposal involve testing of hypothesis: No Yes (describe below)

Primary hypotheses to be tested are:

1. Type 2 immune response after two doses of nOPV2 with bOPV is non-inferior to the immune response observed after two doses of nOPV2 given alone (10% non-inferiority margin).
[Primary objective: 1]
2. Type 1 and 3 immune responses after two doses of bOPV with nOPV2 are non-inferior to the immune responses observed after two doses of bOPV given alone (10% non-inferiority margin).
[Primary objective: 2]

Secondary hypotheses to be tested are:

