1. Type 2 immune responses after one or three doses of nOPV2 with bOPV are non-inferior to the immune responses observed after the same number of doses of nOPV2 given alone (10% non-inferiority margin).
[Secondary objective: 1]
2. Type 1 and 3 immune responses after one or three doses of bOPV with nOPV2 are non-inferior to the immune responses observed after the same number of doses of bOPV given alone (10% non-inferiority margin).
[Secondary objective: 2]

Exploratory questions:

1. What are the shedding rates among vaccine recipients following one dose of nOPV2, bOPV, or co-administered nOPV2 and bOPV?
[Secondary objective: 3]
2. What is the shedding rate among siblings of vaccine recipients following one dose of nOPV2?
[Secondary objective: 4]
3. What is the estimated household transmission rate following one dose of nOPV2?
[Secondary objective: 4]
4. What proportion of vaccine recipients and siblings have intertypic recombinants in stool following one dose of nOPV2 given with or without bOPV? What are the characteristics of the recombinants?
[Secondary objective: 5]

Specific Objectives:

Table 1: Schematic representation of study arms.

Arms		Age of participant						Unadjusted sample size	Enrollment target*
		6 weeks	7 weeks	8 weeks	10 weeks	14 weeks	18 weeks		
A	nOPV2	• nOPV2	▲	▲	▲ • nOPV2	• nOPV2	•	238	265
B	nOPV2/bOPV	• nOPV2 + bOPV		▲	▲ • nOPV2 + bOPV	• nOPV2 + bOPV	•	238	265
C	bOPV	• bOPV		▲	▲ • bOPV	• bOPV	•	238	265
Total								714	795
• Indicates blood collection ▲ Indicates stool collection from participant and from youngest sibling household contact (<10 years of age) Household transmission component * Adjusted for 10% attrition									

Primary objectives*

1. To compare type 2 immunogenicity of two doses of nOPV2 with two doses of nOPV2 co-administered with bOPV.
 - a. nOPV2 at 6 and 10 weeks (A) vs. nOPV2 + bOPV at 6 and 10 weeks (B)
2. To compare type 1 and 3 immunogenicity of two doses of bOPV with two doses of bOPV co-administered with nOPV2.
 - a. bOPV at 6 and 10 weeks (C) vs. nOPV2 + bOPV at 6 and 10 weeks (B)

Secondary objectives*

1. To compare type 2 immunogenicity of one or three doses of nOPV2 with the same number of doses of nOPV2 co-administered with bOPV.
 - a. nOPV2 at 6 weeks (A) vs. nOPV2 + bOPV at 6 weeks (B)
 - b. nOPV2 at 6, 10, and 14 weeks (A) vs. nOPV2 + bOPV at 6, 10, and 14 weeks (B)

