This is an open-label, non-inferiority, randomized clinical trial that will compare immune response to types 1, 2 and 3 polioviruses of nOPV2 and bOPV when co-administered compared to nOPV2 and bOPV given alone. The study will recruit 795 vaccine recipients in three arms. Vaccine recipients will be enrolled at 6 weeks of age and followed until 18 weeks of age, for 12 weeks of follow-up. For each vaccine recipient enrolled, one sibling will be enrolled at the same time and followed for 4 weeks .

General Analytical Issues

The data will be analysed by study investigators that include epidemiologists and statisticians. Statistical packages that will be used for the analysis include R, SAS and STATA.

For assessing immunity to polio, seropositivity is defined as reciprocal polio neutralizing antibody titers

of at least 1:8. Immune response will be defined as either seronegative vaccine recipients ($<1:8$ titers) who become seropositive ($\geq 1:8$) [seroconversion] or vaccine recipients who demonstrate a four-fold

increase in titer (boosting). Baseline maternal antibody titers will be determined at 6 weeks of age and the estimated maternal antibody level at each blood collection will be calculated assuming an exponential decline with a half-life of 28 days.

For assessing fecal viral shedding, detection of nOPV2 or bOPV vaccine virus in stool specimens from vaccine recipient or sibling at either 1, 2, or 4 weeks post-vaccination of the vaccine recipient at 6 weeks of age will be defined as positive for viral shedding. For assessing the detection of household transmission, presence of transmission will be defined as the sibling of the vaccine recipient testing positive for nOPV2 vaccine virus at either 1, 2, or 4 weeks post-vaccination of the vaccine recipient at 6 weeks of age.

To characterize the intertypic recombinants in a subset of stool specimens of vaccine recipients and siblings after one dose of nOPV2 given with or without bOPV, amplicon sequences from long-read sequencing methods will be used to confirm genome structure. Amplicon sequences will also be mapped against all three Sabin vaccine reference sequences to generate coverage plots.

Primary Analytical Approach

The primary analytical approach will be intention-to-treat. To evaluate the primary objectives, the intention-to-treat analysis will be restricted to vaccine recipients who:

- Have not withdrawn consent for receipt of vaccines and follow-up evaluations since enrolment.

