- Have adequate blood specimen for serological analysis from the enrolment visit at 6 weeks of age.
- Have adequate blood specimen for serological analysis from the follow-up visit as mentioned by arm by primary objective in Table 5.

For secondary objectives 1 and 2, the intention-to-treat analysis will be restricted to vaccine recipients who:

- Have not withdrawn consent for receipt of vaccines and follow-up evaluations since enrolment.
- Have adequate blood specimen for serological analysis from the enrolment visit.
- Have adequate blood specimen for serological analysis from the follow-up visit as mentioned by arm by secondary objective in Table 5.

For secondary objectives 3-5, the intention-to-treat analysis will be restricted to vaccine recipients and siblings who:

- Have not withdrawn consent for receipt of vaccines and follow-up evaluations since enrolment.
- Have adequate stool specimens to examine vaccine-virus particles.

Secondary Analytical Approach

In addition to an intention-to-treat analysis, we will also perform per protocol analysis. To evaluate the primary objectives, per protocol analysis will be limited to vaccine recipients with the same restrictions as that outlined in primary analytical approach for primary objectives with additional restrictions of:

- Adequate blood specimen for serological analysis within 3 days of the scheduled visit date. This applies to enrolment visit blood specimen as well as follow-up visit blood collection.
- Received all scheduled study vaccines within 3 days of scheduled visit date.

For secondary objectives 1 and 2, the per protocol analysis will be limited to vaccine recipients with the same restrictions as those outlined in the primary analytical approach for secondary objectives 1 and 2 with additional restrictions of:

- Adequate blood specimen for serological analysis within 3 days of the scheduled visit date. This applies to enrolment visit blood specimen as well as follow-up visit blood collection.
- Received all scheduled study vaccines within 3 days of scheduled visit date.

For secondary objectives 3-5, the per protocol analysis will be limited to vaccine recipients or siblings with the same restrictions as those outlined in the primary analytical approach for secondary objectives 3-5 with additional restrictions of:

- Adequate stool specimen to examine vaccine-virus particles within 3 days of the scheduled visit date.

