- Vaccine recipient received the scheduled study vaccination at 6 weeks of age.

Table 5: Study arms comparison, study endpoints, and results by objective

Study Objective	Study Arms Comparison	Endpoint (vaccine recipient age)	Results Included in Analysis
Primary			
1. To compare type 2 immunogenicity of two doses of nOPV2 with two doses of nOPV2 co-administered with bOPV.	A vs. B	14 weeks	Serology: 6, 10, 14 weeks
2. To compare type 1 and 3 immunogenicity of two doses of bOPV with two doses of bOPV co-administered with nOPV2.	C vs. B	14 weeks	Serology: 6, 10, 14 weeks
Secondary			
1. To compare type 2 immunogenicity of one or three doses of nOPV2 with the same number of doses of nOPV2 co-administered with bOPV.	A vs. B	10 weeks	Serology: 6, 10 weeks
		18 weeks	Serology: 6, 10, 14, 18 weeks
2. To compare type 1 and 3 immunogenicity of one or three doses of bOPV with the same number of doses of bOPV co-administered with nOPV2.	C vs. B	10 weeks	Serology: 6, 10 weeks
		18 weeks	Serology: 6, 10, 14, 18 weeks
3. To assess the presence of fecal viral shedding (as determined by real-time RT-PCR) over time following one dose of nOPV2, bOPV, or co-administered nOPV2 and bOPV.	Descriptive with comparisons of A vs. B and B vs. C	10 weeks (i.e. 4 weeks post-vaccination)	Stool: 7 (Arm A only), 8, 10 weeks from vaccine recipient
4. To estimate household transmission of nOPV2 by assessing the presence of fecal viral shedding (as determined by real-time RT-PCR) among siblings of vaccine recipients.	Descriptive	10 weeks (i.e. 4 weeks post-vaccination)	Stool: 7 (Arm A only), 8, 10 weeks from sibling
5. To assess the occurrence and genomic characteristics of intertypic recombinants in stool specimens of vaccine recipients and siblings after one dose of nOPV2 given with or without bOPV.	Descriptive with comparison of A vs. B	10 weeks (i.e. 4 weeks post-vaccination)	Stool: 8, 10 weeks from vaccine recipient and sibling

Adverse Events (AEs)

Safety will be assessed by:

- Incidence rate of solicited systemic AEs 24–48 hours after the first study vaccination.
- Incidence rate of unsolicited AEs during entire study period.
- Incidence rate of serious AEs during entire study period.

Data Safety Monitoring Plan (DSMP)

Records to be kept

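### Consent and dosing conditions in the analysis sets have no cut-off at the endpoint specimen, so events after that specimen can remove valid results

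*Protocol*

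**What the plan says.** Data Analysis, Primary Analytical Approach, states: "The primary analytical approach will be intention-to-treat". For the primary objectives the set is then restricted in three ways:

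- Consent: "Have not withdrawn consent for receipt of vaccines and follow-up evaluations since enrolment".
- Adequate blood from the 6-week enrolment visit.
- Endpoint blood: "Have adequate blood specimen for serological analysis from the follow-up visit as mentioned by arm by primary objective in Table 5". Table 5 puts this endpoint at 14 weeks.

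The consent condition is repeated for the one- and three-dose comparisons ("For secondary objectives 1 and 2, the intention-to-treat analysis will be restricted to vaccine recipients who"), whose endpoints are at 10 and 18 weeks, and again for the stool objectives 3–5.

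Secondary Analytical Approach adds per-protocol conditions. For the primary objectives and for secondary objectives 1 and 2 these are blood within 3 days of the scheduled date and "Received all scheduled study vaccines within 3 days of scheduled visit date". For objectives 3–5 the dosing condition is narrower: "Vaccine recipient received the scheduled study vaccination at 6 weeks of age".

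Three doses are scheduled, for example "B: nOPV2 + bOPV @ 6, 10, and 14 weeks", whereas the primary type 2 comparison concerns two of them: "nOPV2 at 6 and 10 weeks (A) vs. nOPV2 + bOPV at 6 and 10 weeks (B". Study Procedures and Timing of Evaluations both place blood collection before vaccination at a visit. Follow-up continues to 18 weeks of age.

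**The concern.** An analysis of a 14-week titre should not depend on what a family does after the 14-week blood. As worded, it does: withdrawal between weeks 14 and 18 removes an infant whose primary result rests on adequate specimens. For the 10-week endpoints the exposed period is longer, eight weeks instead of four.

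Parents and staff know the arm (Randomization section), so later withdrawal could differ between arms. Removing infants on that basis gives up some of the comparability that randomisation provides and discards usable data, with no evident gain. In a non-inferiority trial, a loss concentrated among poor responders in the co-administration arm would flatter that arm.

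The per-protocol dosing rule raises the same difficulty. If all scheduled doses means all three, a one-dose result at 10 weeks depends on doses given at 10 and 14 weeks, after its blood was drawn. Two analysts could also build different sets from the same sentence.

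**Working it through.** **1. What the consent clause does beyond the specimen clauses**

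| Infant | Endpoint blood present? | Excluded by specimen clause? | Excluded by consent clause? |
|---|---|---|---|
| Withdraws before week 14 (primary endpoint) | No | Yes | Yes, with no added effect |
| Gives 14-week blood, withdraws before week 18 | Yes | No | **Yes** |
| Gives 10-week blood or stool, withdraws before week 18 (10-week endpoints) | Yes | No | **Yes** |
| 18-week endpoint, completes the last visit | Yes | No | No |

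The clause changes membership only in the two bold rows. In both, the specimens for that endpoint were already collected.

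**2. What the per-protocol dosing rule does**

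- *Two-dose endpoint (week 14).* The third dose follows the endpoint blood at the same visit. A late visit already fails the 3-day blood window, so a late dose adds no exclusion. Only an infant bled on time but not vaccinated at that visit is affected.
- *One-dose endpoint (week 10).* The second dose is given at the same visit as the blood, but the third falls at a separate visit four weeks later. An infant with an on-time first dose and on-time 10-week blood is lost if the 14-week visit is late or missed. The documents give no rate for this; each 1% of 238 is 2.4 infants per arm.
- *Three-dose endpoint (week 18).* All three doses precede the blood, so the rule fits.

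**3. The plan's own sample size**

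Inputs (Sample size section): 85% response for types 1 and 3, margin 0.10, power 90%, alpha 0.05, 10% attrition. The section does not say whether alpha is one- or two-sided; the one-sided reading with a continuity correction gives the stated figure.

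- Uncorrected: n = 2 × 0.85 × 0.15 × (1.645 + 1.282)² / 0.10² = 218.4.
- Corrected: n/4 × (1 + √(1 + 4/(n × 0.10)))² = 237.96, so 238 per arm, as stated.
- Attrition: 238 / 0.90 = 264.4, so 265, as stated.

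**4. Effect on power**

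Assume 2–5% of evaluable infants withdraw between weeks 14 and 18, on top of the planned attrition. Then 2% of 238 = 4.8 and 5% of 238 = 11.9, or about 5 to 12 infants per arm.

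Power = Φ[(0.10 − 1/n) / √(2 × 0.85 × 0.15 / n) − 1.645]

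| Extra loss | n per arm | Power |
|---|---|---|
| 0% | 238 | 90.0% |
| 2% | 233 | 89.4% |
| 5% | 226 | 88.5% |

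For type 2 at 90% response, the same losses move power from 96.7% to 96.4% and 95.9%. With alpha at one-sided 0.025 and 85% response, it moves from 83.3% to 82.5% and 81.2%. The loss is modest in each case.

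**5. Possible bias**

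Suppose one arm only loses a fraction f whose response rate is r, against 0.85 overall. The shift in that arm's observed rate is (0.85 − f·r)/(1 − f) − 0.85.

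- f = 0.05, r = 0.50: 0.825/0.95 − 0.85 = 1.8 points.
- f = 0.05, r = 0.70: 0.815/0.95 − 0.85 = 0.8 points.
- f = 0.01, r = 0.50: 0.845/0.99 − 0.85 = 0.35 points.

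These are one-sided, unfavourable illustrations, set against a 10-point margin.

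**The case against.** **Consent terms may require the exclusion.** Sera are shipped only after the 18-week visits, and the Data Safety Monitoring Board section says blood is analysed after field activities end. For a family that withdraws between weeks 14 and 18, the 14-week result is therefore still an untested specimen. Whether it may be tested afterwards depends on consent terms that are not in the text at hand. This stands: the documents do not show that keeping these infants is always permitted, and the remedy must allow for it. It does not justify a blanket exclusion in the analysis set.

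**The clause may be narrow.** It joins vaccines and follow-up evaluations, so it need not catch a parent who declines a single procedure. That limits how many infants it affects but does not supply a cut-off.

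**The dosing rule has a natural reading by objective.** It sits under objectives defined by particular doses, and secondary objectives 1 and 2 cover both one and three doses, so one sentence has to be generic. That is a plausible intention, but it is not written, and the stool rule shows the protocol naming the relevant dose.

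**A large per-protocol loss for the two-dose endpoint.** A reader might infer that every late or missed 14-week dose costs the primary per-protocol set an infant. The documents do not support this, because dose and endpoint blood share a visit and the blood has its own window.

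**The label.** A reader might infer that the primary set is misrepresented, since a set requiring two specimens and no withdrawal is not intention-to-treat in the strict sense. The restrictions are listed openly beside the label, and renaming the set would change no result.

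**Left to the analysis plan.** Fine detail of analysis sets often is. Here, however, the protocol states the rule, and the stated rule is the difficulty.

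**Conclusion.** The point holds as a wording fault of modest weight. The intention-to-treat consent condition has no end date, and its practical effect on the 14-week primary and the 10-week analyses is to drop infants whose specimens are already in hand. The serology per-protocol dosing rule, taken literally, has a similar effect, mainly on the one-dose endpoint and little on the two-dose endpoint.

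The size rests on an assumed 2–5% withdrawal between weeks 14 and 18 in addition to planned attrition: about 5–12 of 238 evaluable infants per arm and 0.6–1.5 points of power. If attrition by week 14 is below 10%, part of this loss is absorbed. Open-label conduct makes arm-dependent withdrawal possible, so a reader might infer that the primary contrast is biased. Nothing in the documents shows this, and the illustrations give at most 1.8 points against a margin of 10. The reason to act is that the exclusion brings no evident benefit and is easily avoided.

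**What to change.** 1. In each intention-to-treat set, apply the consent condition only up to the endpoint specimen for that objective. Keep infants with adequate baseline and endpoint blood (or adequate stool for objectives 3–5) who withdraw later, unless the parent asks for removal or the consent terms do not allow use of the specimen. Check those terms before finalising the wording.
2. In the serology per-protocol sets, require only the doses scheduled before the endpoint blood: the first for week 10, the first two for week 14, and all three for week 18.
3. Optionally, call the primary set modified intention-to-treat.

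The cost is a few lines of text. No visit, specimen or test is added, and more randomised infants stay in the analysis.

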2. To compare type 1 and 3 immunogenicity of one or three doses of bOPV with the same number of doses of bOPV co-administered with nOPV2.
 - a. bOPV at 6 weeks (C) vs. nOPV2 + bOPV at 6 weeks (B)
 - b. bOPV at 6, 10, and 14 weeks (C) vs. nOPV2 + bOPV at 6, 10, and 14 weeks (B)
3. To assess the presence of fecal viral shedding (as determined by real-time RT-PCR) over time following one dose of nOPV2, bOPV, or co-administered nOPV2 and bOPV.
4. To estimate household transmission of nOPV2 by assessing the presence of fecal viral shedding (as determined by real-time RT-PCR) among siblings of vaccine recipients.
5. To assess the occurrence and genomic characteristics of intertypic recombinants in stool specimens of vaccine recipients and their siblings after one dose of nOPV2 given with or without bOPV.

*Note: For all objectives, timepoints refer to the timing of vaccine administration.

Background of the Project including Preliminary Observations:

Polioviruses are a member of family Picornaviridae in the enterovirus subgroup, and poliomyelitis is an acute infection caused by polioviruses. Polioviruses are transmitted from person to person either faecally or through pharyngeal secretions. There is minimal cross-immunity between the three distinct serotypes of polioviruses (types 1, 2 and 3). After entering the body through the mouth, polioviruses replicate in the gastrointestinal tract for several days or weeks. In the majority of cases, they cause no apparent illness or mild illness including diarrhea, fever, and/or vomiting. In approximately one out of 200 infections, however, polioviruses invade the cells of the spinal cord leading to paralysis of limb(s) or invade brain stem cells affecting the respiratory muscles. Of those individuals with paralytic poliomyelitis, an estimated 5-10% die because of breathing failure. The remaining suffer from lifelong paralysis of one or more limbs. Before the availability of vaccines, poliomyelitis was the leading cause of permanent disability worldwide [1, 2].

Poliovirus Vaccines

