Should a serious illness occur while the vaccine recipient is enrolled in the study (requiring a physician's visit or hospitalization), parents will be instructed to seek medical care immediately and to notify study

staff as soon as possible. Medical care for vaccine recipients will be provided free of charge for expected minor illnesses that develop during the follow up period, such as diarrhea and respiratory infections, as well as any adverse outcomes judged to be possibly, probably or definitely related (detailed below) to study vaccines or vaccination.

Recording, Monitoring and Reporting of Adverse Events

Solicited AEs: In this study, fever, vomiting, crying abnormal, drowsiness, loss of appetite and irritability will be solicited at one timepoint 24-48 hours after the first study vaccination. This will include the definitions of mild, moderate and severe AEs, as described in Table 6, to facilitate the assessments of the level of functional impairment for each experienced AE. For fever, temperature will be recorded if available, otherwise subjective fever will be solicited.

Table 6: Intensity scales for solicited symptoms

Events	Severity Grade			
	0	1	2	3
Fever (if thermometer is available)	<37.5° C	37.5° C- 38.0 ° C	38.1° C- 39.0 ° C	>39.0 ° C
Vomiting	None	1 episode/24 hours	2-5 episodes/24 hours	≥ 6 episodes/24 hours
Abnormal Crying	None	< 1hour	1-3 hours	>3 hours
Drowsiness	None	Sleepier than usual or less interested in surroundings	Not interested in surroundings or did not wake up for a feed	Sleeping most of the time or difficult to wake up
Poor feeding	None	Eating less than normal	Missed 1 or 2 feeds completely	Refuses ≥3 feeds or refuses most feeds
Irritability	None	Easily consolable	Requiring increased attention	Inconsolable

Unsolicited AEs: The investigator will assess the incidence and maximum intensity that occurred over the duration of the event for all unsolicited AEs recorded during the study. The assessment will be based on the investigator's clinical judgment. The intensity should be assigned to one of the following categories:

- 1 (mild) = An AE which is easily tolerated by the subject, causing minimal discomfort and not interfering with everyday activities.
- 2 (moderate) = An AE which is sufficiently discomforting to interfere with normal everyday activities.
- 3 (severe) = An AE which prevents normal, everyday activities.

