4. Drowsiness: No Yes If yes, Grade 1: Sleepier than usual or less interested in surroundings

Grade 2: Not interested in surroundings or did not wake up for a feed

Grade 3: Sleeping most of the time or difficult to wake up

5. Poor feeding: No Yes If yes, Grade 1: Eating less than normal

Grade 2: Missed 1 or 2 feeds completely

Grade 3: Refuses ≥3 feeds or refuses most feeds

6. Irritability: No Yes If yes, Grade 1: Easily consolable

Grade 2: Requiring increased attention

Grade 3: Inconsolable

7. Other Adverse Events (24–48 hours after 6-week vaccination) No Yes

If yes, specify: _____

If yes: Grade 1 (Mild): An AE which is easily tolerated by the participants, causing minimal discomfort and not interfering with everyday activities.

Grade 2 (Moderate): An AE which is sufficiently discomforting to interfere with normal everyday activities.

Grade 3 (Severe): An AE which prevents normal, everyday activities.

If parent responds Yes to any of the above, fill out an AE form.

Name of medical officer: _____ Signature: _____

Household Visit at 7 weeks of Age*To be completed for participants in Arm A only***Home Visit #1: To be completed on the day the stool kits are delivered to the parents.****Date stool kits delivered** (dd/mm/yy): / /

1. Were there any problems in giving the two stool kits to the parents? Yes / No

1a. If yes, explain _____

Name and signature of study staff: _____

Home Visit #2: To be completed on the day the stool samples are picked up.**For vaccine recipient:**

1. Stool sample collected? Yes / No 1a. If no stool obtained, why not? _____

2. Date of stool collection (dd/mm/yyyy): / /

3. Time of collection (hh:mm): :

4. Sufficient quantity (8 grams)? Yes / No 4a. If insufficient, specify reasons: _____

For sibling:

5. Stool sample collected? Yes / No 5a. If no stool obtained, why not? _____

6. Date of stool collection (dd/mm/yyyy): / /

7. Time of collection (hh:mm): :

8. Sufficient quantity (8 grams)? Yes / No 8a. If insufficient, specify reasons: _____

Name and signature of study staff: _____

Data Entry: To be completed when data entered into RedCapDate of data entry in RedCap (dd/mm/yyyy): / /

Name and signature of person entering data: _____

Household Visit at 8 weeks of Age*To be completed for vaccine recipients in all Arms***Home Visit #1: To be completed on the day the stool kits are delivered to the parents.****Date stool kits delivered** (dd/mm/yy): / /

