2b. Date of vaccination (dd/mm/yy): / /
3. Has any other child in the household received OPV since the last clinic visit ? Yes / No 3a. If yes, specify: _____
4. Has the child had diarrhea in the last 24 hours (≥ 3 loose stools in 24 hours)? Yes / No
4a. If yes, specify: duration of diarrhea in days:
(If the child currently has fever $>38.3^{\circ}\text{C}$, blood in stools, vomiting or signs of dehydration, do not continue with study procedures. Provide advice and referral as required.)
5. Has the child been sick since the last study visit? Yes / No 5a. If yes, specify: _____
6. Is the child on any immunosuppressive medications? Yes / No 6a. If yes, specify _____

Physical Exam

7. Temperature: . $^{\circ}\text{Celsius}$
8. Length #1: . cm
9. Length #2: . cm
10. Weight #1: . kg
11. Weight #2: . kg

Blood Collection

12. Blood sample collected? Yes / No 12a. If not, why? _____
13. Sufficient quantity (1 ml)? Yes / No 13a. If insufficient, why? _____
14. Time of collection (hh:mm): :

Vaccine Administration*If Study Arm A or B*

15. nOPV2 administered? Yes / No 15a. If not, reason: _____
If administered: 15b. Time of vaccine administration (hh:mm): :
15c. Expiration (mmm/yy): /

If Study Arm B or C

16. bOPV administered? Yes / No 16a. If not, reason: _____
If administered: 16b. Time of vaccine administration (hh:mm): :
16c. Expiration (mmm/yy): /

Clinic Visit at 10 weeks of Age (ctd.)

17. Pentavalent administered? Yes / No 17a. If not, reason: _____

If administered: 17b. Dose: Penta1 / Penta2 / Penta3

17c. Site of administration: Right thigh / Left thigh

18. PCV administered? Yes / No 18a. If not, reason: _____

If administered: 18b. Dose: PCV1 / PCV2 / PCV3

18c. Site of administration: Right thigh / Left thigh

Observe for 30 minutes after vaccine administration:

19. Any symptoms? Yes / No

19a. If yes, specify (*complete Adverse Event Form, if required*): _____

The following questions correspond to sibling of the study vaccine recipient. Note: the sibling does not need to be present for this visit.

20. Has the child received any poliovirus vaccines (bOPV, fIPV) since last visit? Yes / No

20a. If yes, specify: / /

20b. Date of vaccination (dd/mm/yy): _____

21. Has the child had diarrhea in the last 24 hours (≥ 3 loose stools in 24 hours)? Yes / No21a. If yes, specify: duration of diarrhea in days

22. Has the child been sick since the last study visit? Yes / No 22a. If yes, specify: _____

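### Diarrhoea is not actively solicited and has no event-specific grade after vaccination, although the protocol names it beside fever and vomiting, which are solicited and graded

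*Protocol*

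**What the plan says.** In Recording, Monitoring and Reporting of Adverse Events, "fever, vomiting, crying abnormal, drowsiness, loss of appetite and irritability will be solicited at one timepoint 24-48 hours after the first study vaccination". Table 6 gives each of the six symptoms its own intensity scale, and the 24–48 hour form in Appendix A repeats them (loss of appetite appears as poor feeding). Diarrhoea is in none of the three places.

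The Background describes most poliovirus infections in these terms: "they cause no apparent illness or mild illness including diarrhea, fever, and/or vomiting". The adverse-event part of the Protocol also counts diarrhoea among "expected minor illnesses that develop during the follow up period, such as diarrhea and respiratory infections".

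The clinic-visit forms do carry a diarrhoea item, "Has the child had diarrhea in the last 24 hours", defined as three or more loose stools in 24 hours, with a field for duration in days.

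The 24–48 hour form ends with an open item, "Other Adverse Events (24–48 hours after 6-week vaccination", which has generic Grade 1–3 boxes, and it instructs: "If parent responds Yes to any of the above, fill out an AE form". The investigator is to assess the "maximum intensity that occurred over the duration of the event for all unsolicited AEs recorded during the study".

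The safety measures in the Data Analysis section are incidence rates. The first is "Incidence rate of solicited systemic AEs 24–48 hours after the first study vaccination"; the others cover unsolicited and serious events over the whole study.

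**The concern.** The Background names three mild illnesses together. Two of them are asked about by name after the first dose and graded on scales specific to the symptom. The third, diarrhoea, is not, although it is an obvious symptom to ask about after a live vaccine that replicates in the gut.

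The Safety Monitoring section justifies the 24–48 hour contact by the newness of nOPV2, and the Justification section says that co-administration with bOPV has not been studied before. What is at stake is how consistently lower-gut symptoms are ascertained in that setting. A general question depends on what the parent thinks worth mentioning, and here parents and staff know the arm. A symptom asked about by name, with a stated definition, leaves less to that judgement. Relatedness is judged partly on timing after vaccination, and clusters of at least three events go to the safety board. Both uses depend on even ascertainment and known onset dates.

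**Working it through.** The plan states no figure on this point, so there is none to reproduce. The check sets the relevant places side by side.

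**Step 1. The three illnesses named in the Background.**

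| Symptom | Solicited list | Scale in Table 6 | 24–48 hour form |
|---|---|---|---|
| Fever | yes | temperature bands | named, graded |
| Vomiting | yes | episodes per 24 hours | named, graded |
| Diarrhoea | no | none | not named |

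**Step 2. Every route by which diarrhoea in a vaccinated infant can be recorded.**

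| Route | Window | Diarrhoea named? | Grade |
|---|---|---|---|
| Open item 7, 24–48 hour form | since the 6-week visit | no | generic 1–3, triggers AE form |
| AE questioning at each clinic visit | since previous visit | no | generic mild/moderate/severe on AE form |
| Sickness item, 10-, 14- and 18-week forms | since previous visit | no | none on the item (free text) |
| Diarrhoea item, 10-, 14- and 18-week forms | last 24 hours | yes, with definition | none (duration in days) |
| Household stool-collection forms (7 weeks in Arm A; 8 and 10 weeks in all arms) | – | no symptom question | – |

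The diarrhoea item on the 6-week form is placed ahead of vaccination, so it describes the child before the first dose.

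**Step 3. Size of the window.** Clinic visits at 6, 10, 14 and 18 weeks are 4 × 7 = 28 days apart. The defined diarrhoea item covers 1/28 = 3.6% of each interval, and that day lies about four weeks after the preceding dose. The duration field extends back only for an episode still present in that last day; one that ended earlier does not trigger the item. The 3.6% belongs to this item alone, since the two general routes cover all 28 days.

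**Step 4. Reach of the solicited contact.** Follow-up is 12 × 7 = 84 days. A contact 1 to 2 days after the first dose reaches back over 1/84 = 1.2% to 2/84 = 2.4% of it, and there is no such contact after the second or third dose. The Background puts replication in the gut at several days or weeks. Adding diarrhoea to the 24–48 hour form alone would therefore catch only early events.

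**Result.** No route combines three things: diarrhoea asked about by name, a window covering the period after a dose, and a grade specific to the symptom. The routes that cover the period are general, and the one that names the symptom covers a single late day.

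**The case against.** The strongest reply is that diarrhoea is not lost. A reader might infer from its absence from the solicited list that the trial has no graded measure of it, or that it can enter the data only as a volunteered remark at 24–48 hours. The Protocol supports neither reading. Item 7 has Grade 1–3 boxes and leads to an adverse-event form. All unsolicited events are graded. Staff question parents at every clinic visit about events since the last one, and three forms ask whether the child has been ill in the interval. Parents also have a number to call. This stands in full and limits the point to the lack of a specific prompt and a specific scale.

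A reader might also infer that a planned safety comparison between arms is compromised. The Protocol lists incidence rates only, states no safety objective or between-arm test, and sizes the trial for immunogenicity. That stands too.

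Third, the Background sentence concerns poliovirus infection in general. It does not show diarrhoea to be an expected reaction within 48 hours of nOPV2 or bOPV, and the Protocol elsewhere treats diarrhoea as an ordinary illness of follow-up, which fits handling it as unsolicited. This is fair, and it is why a 24–48 hour item alone is not enough.

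Fourth, the 24-hour item also serves to check the child's condition on the day, for which short recall is right. It should be kept. Lastly, prompted answers are unblinded as well. That is so, but a defined symptom asked of every parent leaves less to what is volunteered.

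What remains is that general questions do not replace a named and defined symptom.

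**Conclusion.** The point holds as a modest limit on safety ascertainment. Diarrhoea after vaccination has no active prompt over the period after a dose and no event-specific grade, while fever and vomiting, named beside it in the Background, have a prompt and a scale after the first dose. It is neither an internal contradiction nor a missing measure: the list, Table 6 and the form agree with one another, and generic capture and grading exist. It does not affect the immunogenicity results.

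The likely consequence is under-recorded or unevenly recorded diarrhoea. By how much cannot be derived from the Protocol, which gives no expected rate. The conclusion assumes that the Appendix A forms are used as printed and that interviewers do not routinely name diarrhoea when asking the general questions. If they do, the gap is smaller and the practice only needs writing down.

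**What to change.** Add diarrhoea to the solicited list, to Table 6 and to the named items of the 24–48 hour form. Use the definition already on the clinic forms (three or more loose stools in 24 hours) and an event-specific intensity scale, as vomiting already has.

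On the 10-, 14- and 18-week forms, keep the 24-hour item and add a question on diarrhoea since the last clinic visit, with date of onset. This second change matters because the early contact cannot see later episodes. Report diarrhoea incidence by arm, descriptively, with the other solicited events and over the follow-up intervals.

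The cost is one more question at a contact already planned, one extended item on three existing forms, and one row in Table 6. The downside is a few more minor adverse-event reports to process. No extra visit or specimen is needed, and the sample size does not change.
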